## Randomization

As discussed above, randomization was to be stratified on the study year of implementation (Y1 vs. Y2). The 9 Y1 sites were randomly assigned to begin active implementation in one of 3 waves (3 sites per wave). Within Y2, the 4 implementation waves were to consist of 2 waves with 3 sites each, and 2 waves with 2 sites each. Given the requirements above that the last wave have just two sites and that one Y2 site needed to be in a wave with just one other site (we will refer to this site as site A), we developed a randomization scheme to ensure that each site had the same probability of being assigned to each wave (0.2 probability to be assigned to Y2 wave 4 and 0.8/3 each for waves 1-3 of Y2) as follows. First, we randomly selected one of the first 3 waves to be the other 2-site wave. Then, we randomly assigned site A to wave 4 with probability 0.2 or to the other 2-site wave with probability 0.8. The remaining 9 Y2 sites were then to be randomly assigned to the other available slots. Under this randomization scheme, letting B denote an arbitrary site different from site A, we have:

- $P(\text{site A assigned to wave 4}) = 0.2$
- $P(\text{site B assigned to wave 4}) = P(\text{site B assigned to wave 4} \mid \text{A assigned to wave 4}) * P(\text{A assigned to wave 4}) + P(\text{site B assigned to wave 4} \mid \text{A not assigned to wave 4}) = 1/9 * 0.2 + 2/9 * 0.8 = 0.2$
- $P(\text{site A assigned to wave } j) = P(\text{wave } j \text{ assigned to be the other 2-site wave}) * P(\text{site A assigned to wave } j \mid \text{wave } j \text{ assigned to be the other 2-site wave}) = 1/3 * 0.8, \text{ for } j = 1, 2, 3$
- $P(\text{site B assigned to wave } j) = 1/3 * [1 - P(\text{site A assigned to wave } j)] = 0.8/3, \text{ for } j = 1, 2, 3$

[figure not shown]
## Allocation concealment

The random allocation sequences were generated by the study biostatistician ([name]) after all of the KPWA sites were identified, including the pairing of clinics within 3 of the sites. Y1 sites were randomized to waves on January 22, 2016 and Y2 sites were randomized on October 7, 2016. The assigned waves are shown in **Table 1** below.

## Study sample

Our base study population consists of patients who had at least 1 visit to one of the 22 KPWA clinics during the period from January 1, 2015 to July 31, 2018, which consists of the period from approximately 1 year prior to the randomization date of the Y1 sites (January 22, 2016) through the end of active implementation in the last wave of sites.

## SPARC Implementation stages

Implementation time windows of interest are shown in **Figure 2**. The “preparatory period” is defined as the period 2 months prior to the SPARC launch date up until the launch, and the “active

implementation” period is defined as the period from 1-4 months after the SPARC launch date at a given site. We will refer to the period up to and including the preparatory period as the “pre-implementation” period, and the period starting with the launch date as the “post-implementation” period. Following intention-to-treat principles, unless otherwise specified, these pre- and post-implementation periods will be defined based on the launch dates during which active implementation was planned to occur (shown in **Table 1**), rather than the actual date when the site begins implementing SPARC (if implementation was delayed).

**Table 1.** Implementation wave dates and randomized assignments of sites to waves

Year	Wave	Site (masked)	Launch Date
Y1	1	Site A	April 4 th , 2016
Y1	1	Site B	April 11 th , 2016
Y1	1	Site C	April 18 th , 2016
Y1	2	Site D	September 7 th , 2016
Y1	2	Site E	September 12 th , 2016
Y1	2	Site F	September 19 th , 2016
Y1	3	Site G	January 4 rd , 2017
Y1	3	Site H	January 9 th , 2017
Y1	3	Site I	January 16 th , 2017
Y2	4	Site J	April 24 th , 2017
Y2	4	Site K	April 24 th , 2017
Y2	4	Site L	April 24 th , 2017
Y2	5	Site M	August 14 th , 2017
Y2	5	Site N	August 14 th , 2017
Y2	5	Site O	August 14 th , 2017
Y2	6	Site P	December 4 th , 2017
Y2	6	Site Q	December 4 th , 2017
Y2	7	Site R	April 9 th , 2018
Y2	7	Site S	April 9 th , 2018

### Outcome measures and time frames

The main primary and secondary outcome measures, as described in the Protocol Paper, are defined in **Table 2** below. Indicator variables for each outcome are created at the level of the primary care visit (since a patient may have multiple primary care visits during the study period). Measures are then aggregated into time-intervals (e.g., weekly or monthly). For the primary analysis, measures are aggregated into 28-day intervals (hereafter referred to as “months”), defined relative to the official launch date of SPARC within the clinic (denoted by T0). For example, the co-primary alcohol brief intervention measure aggregated at the monthly level is defined as the proportion of patients seen in the month who had a brief intervention (defined in **Table 2**) at any point during that month.

**Table 2.** SPARC Trial Primary, Secondary and Other Outcomes from EHR and Claims Data

Category	Measure	Description
Primary Outcomes		

Prevention	Alcohol Brief Intervention	Indicator for whether a patient had a brief intervention documented in the EHR* on the day of, or in the 14 days following a PC visit, and had a positive alcohol screen on the day of the visit or in the prior 365 days*
Treatment	Treatment for Newly Diagnosed AUD (NCQA 2017 alcohol and drug treatment measure)	Indicator for whether a patient had a new AUD diagnosis* and initiated and engaged in AUD treatment*
Intermediate Outcomes		
Prevention	Alcohol screening documented	Indicator for whether a patient had AUDIT-C screening documented in the EHR on the day of the visit or in the prior 365 days
Prevention	Positive alcohol screen	Indicator for whether a patient screened positive on the AUDIT-C (3–12 women and 4–12 men), on the most recent screen documented on the day of the visit or in the prior 365 days
Prevention	High positive alcohol screen	Indicator for whether a patient had a high-positive AUDIT-C score (7–12 points), on the most recent screen documented on the day of the visit or in the prior 365 days
Assessment	Assessed for DSM-5 AUD symptoms	Indicator for whether a patient with a high-positive screen in the past year completed an AUD Symptom Checklist on the day of the visit or in the prior 365 days
Identification	Past-year AUD diagnosis	Indicator for whether a patient had an AUD diagnosis defined as an ICD code for an AUD diagnosis per NCQA anywhere in or outside KPWA (e.g. includes claims) on the day of the PC visit or in the prior 365 days
Identification	New AUD diagnosis	Indicator that a “past-year AUD diagnosis” (defined immediately above) was new on the day of the PC visit, based on no AUD diagnosis in the prior 365 days
Treatment	Initiation of AUD treatment (NCQA)	Indicator for whether a patient received a “new AUD diagnosis” (defined above) and initiated AUD treatment in the following 14 days, per HEDIS ICD codes
Treatment	Engagement in AUD treatment (NCQA)	Indicator for whether a patient who initiated AUD treatment (defined above) had another 2 treatment visits in the following 30 days after initiation (“engagement”) per HEDIS ICD codes

\* Definitions based on intermediate outcomes;

EHR, electronic health record; HEDIS, Healthcare Effectiveness Data and Information Set; NCQA, U.S. National Committee for Quality Assurance

For each outcome measure above, we will perform the following comparisons of the monthly outcome rates (see **Figure 2** for definitions of implementation periods):

**Primary:** before vs. after the start of the active implementation period

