Prevention	Alcohol Brief Intervention	Indicator for whether a patient had a brief intervention documented in the EHR* on the day of, or in the 14 days following a PC visit, and had a positive alcohol screen on the day of the visit or in the prior 365 days*
Treatment	Treatment for Newly Diagnosed AUD (NCQA)	Indicator for whether a patient had a new AUD diagnosis* and initiated and engaged in AUD treatment*
Intermediate outcomes		
Prevention	Alcohol screening documented	Indicator for whether a patient had AUDIT-C screening documented in the EHR on the day of the visit or in the prior 365 days
Prevention	Positive alcohol screen	Indicator for whether a patient screened positive on the AUDIT-C (3–12 women and 4–12 men)
Prevention	High-positive alcohol screen	Indicator for whether a patient had a high-positive AUDIT-C score (7–12 points)
Assessment	Assessed for DSM-5 AUD symptoms	Indicator for whether a patient with a high-positive screen completed an AUD Symptom Checklist on the day of the visit or in the prior 365 days
Identification	Past-year AUD diagnosis	Indicator for whether a patient had an AUD diagnosis defined as an ICD code for an AUD diagnosis per NCQA anywhere in or outside KPWA (e.g. includes claims) on the day of the PC visit or in the prior 365 days
Identification	New AUD diagnosis	Indicator that a “past-year AUD diagnosis” (defined immediately above) was new on the day of the PC visit, based on no AUD diagnosis in the prior 365 days
Treatment	Initiation of AUD treatment (NCQA)	Indicator for whether a patient received a “new AUD diagnosis” (defined above) and initiated AUD treatment in the following 14 days, per HEDIS ICD codes
Treatment	Engagement in AUD treatment (NCQA)	Indicator for whether a patient who initiated AUD treatment (defined above) had another 2 treatment visits in the following 30 days after initiation (“engagement”) per HEDIS ICD codes

*Definitions based on intermediate outcomes.

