**Secondary:**

- (1) active implementation vs. pre period
- (2) sustainment period vs. pre period
- (3) sustainment period vs. active implementation

ADDENDUM NOTE: We plan to report analyses of these secondary time periods in a second manuscript.

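### With a 365-day look-back and a 4-month active phase, the sustainment contrasts on alcohol screening measure past-year coverage, not whether clinics kept screening after coaching ended

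*SAP*

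**What the plan says.** SAP Table 2 (Outcome measures and time frames) scores alcohol screening as present if the patient had "AUDIT-C screening documented in the EHR on the day of the visit or in the prior 365 days". Protocol Table 3 defines it the same way. In the SAP, positive and high-positive screens are scored "on the most recent screen documented on the day of the visit or in the prior 365 days", whereas Protocol Table 3 states no look-back for these two. The checklist measure, for patients whose AUDIT-C was high-positive within the past year, records whether they "completed an AUD Symptom Checklist on the day of the visit or in the prior 365 days". Past-year AUD diagnosis counts a code "on the day of the PC visit or in the prior 365 days". New AUD diagnosis is different: it must be new at the visit, "based on no AUD diagnosis in the prior 365 days".

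The SAP continues: "For each outcome measure above, we will perform the following comparisons of the monthly outcome rates". Its secondary list includes sustainment against the pre period and "3) sustainment period vs. active implementation". The Primary analysis section implements these by replacing the before/after indicator with a three-level phase variable, and the calendar trend is modelled in 4-month periods. Active implementation is the four months after launch (SAP, SPARC Implementation stages). Sustainment follows, once the practice coach has left (Protocol, Practice coaches work with interdisciplinary local implementation teams).

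**The concern.** The look-back is about three times as long as the active phase. During active implementation it reaches mostly into pre-launch time. During sustainment it reaches into the coached period. A patient screened by a coached team in month 2 still counts as screened at a visit ten months later, whatever the clinic has done since. Coverage also keeps filling through the active phase, so the active-phase average understates what the clinic is doing and the sustainment average inherits the result.

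The calendar terms cannot remove this, because the carry-over depends on time since each site's own launch and launches are staggered.

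Whether care continued after coaching ended is the question that sustainment contrasts are read to answer. Here the sustainment-versus-active contrast can report improvement when practice is flat, and little or no loss when practice has fallen.

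**Working it through.** **Plan's own figures.** The documents give no size or power figure for the sustainment contrasts or the intermediate outcomes. The only stated figure is power for the primary contrast. It can be reproduced (brief intervention, +7.1 per 10,000: 0.804 against the stated 0.80) but does not bear on this point.

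**Step 1: window arithmetic, with no behavioural assumptions.** Inputs: the 19 launch dates in SAP Table 1, data end July 31, 2018 (SAP, Study sample), active phase 4 × 28 = 112 days, window 366 days (visit day plus 365). Count launch as day 0.

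- Active site-days: 19 × 112 = 2,128.
- Sustainment site-days: waves 1–3, 2,190 + 1,726 + 1,369 = 5,285; wave 4, 3 × 352 = 1,056; wave 5, 3 × 240 = 720; wave 6, 2 × 128 = 256; wave 7, 2 × 2 = 4. Total 7,321.
- Post-launch share of the window on day d is min(d + 1, 366)/366. The mean over days 0–111 is 56.5/366 = 15.4%. The mean over the sustainment site-days is 80.2%.
- The window touches the active phase up to day 111 + 365 = 476, which is at most 365 sustainment days per site: 9 × 365 + 1,056 + 720 + 256 + 4 = 5,321, and 5,321/7,321 = 72.7%.
- It contains the whole active phase up to day 365, which is at most 254 sustainment days per site: 9 × 254 + 3 × 254 + 720 + 256 + 4 = 4,028, or 55.0%.
- The remaining 2,000 site-days (27.3%) all come from the nine Y1 sites.

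**Step 2: effect on the screening measure, by simulation.** Sites have their actual launch dates. A patient is due if there is no screen in the prior 365 days, and a due patient is screened at a visit with probability p0 before launch, pa in the active phase and ps in sustainment. The documents give no visit rates or per-visit probabilities, so these are assumptions: 2, 3 or 5 visits a year (gamma spread, shape 2), p0 from 0.02 to 0.10, pa 0.5 or 0.8. With 3 visits a year and p0 = 0.02, pre-launch coverage is about 10%, near the 8.9% in the Protocol (Setting). Proportions for that case:

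| pa to ps | Look-back: active | Look-back: sustainment | Ratio | Due patients only: active to sustainment |
|---|---|---|---|---|
| 0.5 to 0.5 | 0.65 | 0.82 | 1.27 | 0.53 to 0.54 |
| 0.5 to 0.25 | 0.64 | 0.65 | 1.00 | 0.53 to 0.28 |
| 0.8 to 0.8 | 0.88 | 0.95 | 1.08 | 0.82 to 0.81 |
| 0.8 to 0.4 | 0.88 | 0.79 | 0.89 | 0.83 to 0.43 |
| 0.8 to 0 | 0.88 | 0.36 | 0.41 | 0.82 to 0 |

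Due-only rates lie slightly above the per-visit probability because a patient may have several visits in a month.

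Over all assumptions, sustainment against active on the look-back measure (odds ratios from a binomial model with site, 4-month period and phase terms):

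- Unchanged practice: ratio 1.04–1.27.
- Halved: ratio 0.83–1.03, odds ratio 0.38–1.22 (0.38–0.68 when pa = 0.8). The due-only ratio is about 0.50–0.54.
- Stopped: ratio 0.32–0.50, odds ratio 0.09–0.48. In the first nine sustainment months 52–81% of the active level remains.

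Sustainment against pre after a complete stop: odds ratio 13.5–39 at p0 = 0.02 and 1.5–2.8 at p0 = 0.10. At 3 visits, p0 = 0.10 and pa = 0.8, the crude sustainment rate (0.33) is slightly below pre-launch (0.36), while the adjusted odds ratio is 2.7. This contrast is therefore sensitive to both baseline and adjustment.

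**Step 3: a plain monthly rate does not repair it.** With practice unchanged at pa = ps = 0.8, the share of all patients seen who are screened that month falls from 0.56 to 0.23, because fewer are due.

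**The case against.** The programme implements annual screening, so screened in the past year is a natural measure of coverage, and a rise as coverage fills is real on that estimand. This stands: the measure is not wrong, but it answers a different question from the one the sustainment contrast will be read to answer.

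The Protocol insists on a population-based denominator because implementation changes who is screened and who screens positive. Due-only denominators depend on earlier screening. This also stands, and is why both versions should be reported.

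The Protocol itself is narrower than the SAP. It compares primary outcomes across phases and only describes screening and positive screens over them. An SAP addendum note defers the phase comparisons to a second manuscript. The SAP also plots site-specific crude rates by month, where later decay might show, and Additional file 1, with further sensitivity analyses, is not among the documents. These points lower the stakes but do not change what the SAP's contrasts estimate.

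A reader might infer that screening could stop altogether and still look sustained against the active phase. The arithmetic does not support that: the average falls to less than about half the active level. Nor is halving always hidden; from 80% it is muted but visible. A reader might also carry the simulated sizes over to the other measures, but only screening was simulated. Past-year AUD diagnosis is a prevalence measure by design, and Table 2 already holds its incident counterpart. Finally, nothing here touches the two primary outcomes before versus after launch: neither the brief intervention nor the treatment event is itself carried forward for 365 days.

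**Conclusion.** The concern holds for the sustainment contrasts on alcohol screening and, because they share the window, in kind for positive screen, high-positive screen and the symptom checklist. The imbalance in the look-back (15% against 80% post-launch, 73% of sustainment site-days reaching into the active phase) follows from the SAP's own dates with 28-day months. The consequences for the estimates rest on assumed visit and screening rates and on a model with fixed site effects and no person effect, a simplification of the SAP's mixed model. Across that range the direction is consistent. Sustainment versus active tends to rise when practice is unchanged and shows a muted fall, or none, when screening of due patients halves. It falls clearly when screening stops. Sustainment versus pre may still favour the programme after a stop, by an amount that depends on the pre-launch screening rate. This is a should-change point on secondary contrasts.

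**What to change.** In the SAP's list of secondary comparisons and the matching paragraph of the Primary analysis section:

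- Keep the 365-day population-based measures and label them as coverage.
- Add a due-based screening measure for sustainment conclusions. The denominator is patients seen in the 28-day month with no AUDIT-C in the 365 days before their first visit that month; the outcome is an AUDIT-C documented that month.
- Report positive and high-positive results within that same due denominator, and checklist completion among patients newly high-positive that month.
- Use New AUD diagnosis, not past-year AUD diagnosis, for the diagnosis contrast.
- Optionally, add a sensitivity analysis limited to sustainment months from about day 477 after launch (112 + 365), where the look-back lies wholly in sustainment. Only Y1 sites contribute.

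The cost is SAP wording and a few variables derived from data already extracted, for analyses not yet due in the main paper. The drawback is smaller denominators that depend on earlier screening, so the coverage and due-based versions should appear side by side.

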**Secondary:**

- (1) active implementation vs. pre period
- (2) sustainment period vs. pre period
- (3) sustainment period vs. active implementation

ADDENDUM NOTE: We plan to report analyses of these secondary time periods in a second manuscript.

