Protocol

Title: Sustaining Patient-centered Alcohol-related Care (SPARC)

NCT: NCT02675777

[figure not shown]
Dated: 5/2/2018

Last updated: 8/19/2022

The Sustained Patient-centered Alcohol-related Care (SPARC) trial

The Sustained Patient-centered Alcohol-related Care (SPARC) trial is testing implementation strategies to improve clinical care for unhealthy alcohol use (Fig. 1). To address gaps in preventive clinical care, the SPARC implementation intervention was designed to implement annual alcohol screening followed by brief intervention. To address gaps in clinical care of AUD (i.e., diagnosis and treatment), the SPARC implementation intervention was designed to implement routine assessment of DSM-5 AUD symptoms among PC patients with high-risk drinking and shared decision-making about evidence-based treatment options for those with active AUDs (e.g., medications and/or counseling in PC, as well as assistance accessing other AUD treatments). This alcohol-related care is referred to as “SPARC Clinical Care” hereafter (Fig. 1).

Fig. 1

The SPARC trial: SPARC implementation intervention and alcohol-related clinical care. The SPARC implementation intervention is designed to implement improved alcohol-related clinical care including preventive screening and brief intervention for unhealthy alcohol use and increased AUD diagnosis and treatment.

The SPARC implementation intervention includes three strategies designed to support sustained delivery of the above SPARC clinical care: EHR clinical decision support; performance monitoring and feedback; and front-line support from practice coaches with expertise in alcohol-related care (Fig. 1). These strategies built on lessons learned from the VA [37,38,39, 61], and were refined in a pilot study in three Kaiser Permanente Washington (KPWA) clinics in 2015 [62].

This report describes the protocol for the SPARC trial, a pragmatic, cluster-randomized, stepped-wedge trial testing the SPARC implementation intervention in 22 PC clinics of KPWA. The trial is pragmatic because front-line clinical teams implement all changes in clinical care. A cluster-randomized trial is appropriate because the implementation intervention is conducted at the clinic

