The SPARC implementation intervention is a multicomponent intervention that builds on strategies known to be effective [\[63\]](#). Two strategies were effective in implementing SBI in VA, and a third was added to address barriers to adoption and implementation highlighted in the VA [\[41, 44, 45, 46\]](#). The SPARC implementation intervention integrates (1) EHR decision support [\[64\]](#), (2) performance monitoring and feedback [\[65\]](#), and (3) front-line support by practice coaches to address limitations of the VA approach [\[63, 66\]](#). Specifically, front-line support of PC teams by practice coaches address PC adopters' needs including overcoming stigma, improving knowledge about evidence-based alcohol-related care, and increasing staff ownership about the value of providing their patients alcohol-related care. Practice coaches work with each clinic for about 2 months before implementation and about 4 months after (Fig. [2](#)). Throughout the trial, weekly formative evaluation meetings are used to identify refinements to the implementation intervention, if needed, as well as barriers and facilitators to address and capitalize on, respectively.

- 1) *EHR decision support.* EHR decision support was developed to guide screening for, assessing, and managing unhealthy alcohol use (Table [1](#)) [\[64\]](#). EHR tools are described in detail in an additional file [see Additional file [1](#)]). Briefly, EHR prompts alert medical assistants (MAs) or other staff who room patients (MAs hereafter) to give patients a seven-item paper behavioral health screen, which includes the three-item Alcohol Use Disorders Identification Test-Consumption (AUDIT-C). Based on AUDIT-C results, the EHR alerts the MA to give providers a handout on alcohol use and health for patients needing a brief intervention (if AUDIT-C ≥ 3 points women or ≥ 4 men), and/or to ask patients to complete the paper Alcohol Symptom Checklist, which includes 11 questions based on DSM, 5th Edition (DSM-5) AUD criteria (if AUDIT-C 7-12). EHR prompts were also developed to alert providers about the need for a “warm handoff” to an LICSW or to schedule follow-up care to initiate treatment for patients with new AUDs. The EHR

also prompts MAs at future visits to ask patients with an AUD diagnosis to complete a “monitoring tool” that includes the AUDIT-C.

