To evaluate the impact of the SPARC intervention on sustained receipt of evidence-based alcohol-related care, we are conducting a pragmatic stepped-wedge trial in 22 KPWA PC clinics (Fig. 3). A stepped-wedge approach [68] was chosen so that all clinics would eventually receive the intervention and because providing practice coaches for more than four clinics at a time was not feasible. The trial has seven waves staggered by 4 months, such that the final 2 months of the active implementation phase of one wave overlaps with the preparation phase of the next wave. The sample for the study is patients 18 years of age and older who have a PC visit in one of the 22 participating clinics during the study period.

Fig. 3

SPARC stepped-wedge pragmatic clinical trial design. *Usual care start: January 1, 2015. **Data collection end date: July 31, 2018. Twenty-two clinics (with three paired to create 19 randomized clinical sites total) were randomized across seven waves with stratification (three waves year 1 and four waves years 2–3). Clinics in square bracket are paired as one site.

Randomization

Stratified randomization was used, with 9 clinics randomized in year 1 (three sites in each of three waves), and the remaining 13 clinics randomized in years 2–3 (Fig. 3). Clinics randomized in year 1 are referred to as Y1 sites and those randomized in years 2–3 as Y2 sites. The random assignment to study wave within Y1 and Y2 was generated using a computer-generated list of random numbers by the study biostatistician after all sites were recruited. An additional file describes our randomization scheme and rationale in detail [see Additional file 1].

Four phases of the SPARC trial

Figure 2 shows the four phases of implementation in each clinic. As above, each clinic has approximately 6 months of support from practice coaches, including up to 8 weeks in the “preparation” phase, before the official launch date of SPARC/Behavioral Health Integration,

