Samples and time intervals. A population-based denominator is used in all analyses as the least-biased denominator because clinical site implementation of the SPARC and Behavioral Health Integration interventions is expected to change the proportion and characteristics of patients screened, the proportion who screen positive for unhealthy alcohol use, and the proportion and characteristics of those diagnosed with AUDs. Unless otherwise specified, the sample for each measure is the set of patients who have a PC visit to a PC clinical site for any reason during each

time interval used in analyses. Time intervals used in analyses are typically 4 weeks (i.e., 28-day intervals before and after each clinic's specified launch date). This interval is selected to provide adequate numbers of outcomes per interval [62]. Specifically, primary analyses will compare the monthly (28-day) proportion of patients with each outcome in the pre- versus post-implementation periods.

Statistical analysis

Main analyses of the trial compare two primary outcomes—alcohol SBI and AUD treatment—among PC patients seen in the participating PC clinics before and after the randomized SPARC launch (Fig. 2 and Table 4). Primary analyses will compare the monthly outcome rates of the two primary outcomes before and after launch. Secondary analyses will also compare primary outcomes across other study phases (Fig. 2 and Table 4).

Table 4 The primary analysis

Primary analyses compare months before vs. months after the assigned launch date (usual care + preparation phases vs. active implementation + sustainment phases).
Secondary analyses
a. Usual care vs. active implementation
b. Usual care vs. sustainment
c. Active implementation vs. sustainment

Analyses will follow the general framework for analyzing data from a stepped-wedge trial [70, 71]. The intervals used in analyses are 28-day periods (“month” hereafter) before and after the launch date for each clinic. Specifically, we will model indicator variables for the primary outcomes monthly (e.g., indicator for whether each patient who had a PC visit that month received alcohol SBI or a new AUD diagnosis and treatment) using the following logistic mixed-effect model:

$$\text{logit } P(Y_{ijm} = 1) = \alpha + \beta Int_{jm} + \gamma S_j + f(cm) + b_j + u_i,$$

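### The sustainment versus active contrast on brief intervention is confounded with depletion of patients due for annual screening, so a fall need not mean lost delivery

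*SAP*

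**What the plan says.** The Protocol's opening section says the intervention was "designed to implement annual alcohol screening followed by brief intervention". Under EHR decision support it adds: "Based on AUDIT-C results, the EHR alerts the MA to give providers a handout on alcohol use". The only repeat AUDIT-C described there for later visits concerns patients with an AUD diagnosis.

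SAP Table 2 defines the BI outcome as a "brief intervention documented in the EHR* on the day of, or in the 14 days following a PC visit", together with a positive screen that day or in the prior 365 days. The screening measure is "AUDIT-C screening documented in the EHR on the day of the visit or in the prior 365 days". Both are taken over every patient with a primary care visit in the 28-day month (Protocol, Samples and time intervals; SAP, Outcome measures and time frames).

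The evaluation aim is "sustained receipt of evidence-based alcohol-related care" (Protocol, Study design and sample). Protocol Table 4 lists "c. Active implementation vs. sustainment", and the SAP has the same comparison, "sustainment period vs. active implementation", as item 3 of its secondary comparisons. It is tested by replacing the before/after indicator with a three-level period term (SAP, Primary analysis). An addendum defers these secondary periods to a second manuscript.

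**The concern.** At launch few patients have a past-year screen: 8.9% in three clinics (Protocol, Setting) or 19% in the power assumptions. Almost everyone seen in the first four months is therefore due, and can trigger the BI alert. Later, many patients seen were screened within the year. They are not prompted, but they stay in the denominator.

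The boundary between the two phases is also the date coaching ends, so the drop in patients due coincides with the withdrawal that the contrast is meant to test. An apparent decay in BI after coaching, alongside apparently better screening, could arise without any change in staff behaviour. Nothing in the documents we can read separates patients not due from care not delivered. The alternate BI definitions in the SAP (60-day window, NCQA codes, primary care only) do not address it.

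**Working it through.** **1. The plan's own figures.** The documents give no figure for this contrast. Their BI power concerns the primary before/after comparison and reproduces. The Hussey and Hughes variance with 19 sites, 8 periods, 4 × 1,205 = 4,820 patients per site-period and ICC 0.001 gives 0.803 at +7.1 and 0.897 at +8.2 per 10,000, against 80% and 90% stated.

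**2. Calendar.** Complete 28-day months from each SAP Table 1 launch date to 31 July 2018:
- Wave 1: 30 + 30 + 29 = 89
- Waves 2 to 5: 3 × 24, 3 × 20, 3 × 16 and 3 × 12 = 72, 60, 48 and 36
- Waves 6 and 7: 2 × 8 and 2 × 4 = 16 and 8

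The total is 329 site-months: 19 × 4 = 76 active and 253 sustainment. Post-launch months 5 to 13 supply 12 × 9 + 3 × 8 + 2 × 4 = 140 of the 253 (55%). Over half of sustainment thus lies within a year of launch, when patients screened since launch are not yet due again.

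**3. Closed form for the share of visits due.** Assume λ visits per patient per year (Poisson), nobody screened at launch, and every due visit screened. In year 1 a visit at time t is due only if it is the first since launch, with probability exp(−λt). Let a = 112/365 = 0.307.
- Active: (1 − e^(−λa)) / (λa)
- Rest of year 1: (e^(−λa) − e^(−λ)) / (λ(1 − a))
- Long run: 1/(1 + λ)

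For λ = 2: (1 − 0.541)/0.614 = 0.747; (0.541 − 0.135)/1.386 = 0.293; 1/3 = 0.333.

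| λ | Active | Rest of year 1 | Long run |
|---|---|---|---|
| 1 | 0.861 | 0.531 | 0.500 |
| 2 | 0.747 | 0.293 | 0.333 |
| 3 | 0.654 | 0.168 | 0.250 |

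**4. Simulation with constant behaviour after launch.** From the documents: 19% screened at launch and the calendar in step 2. Assumed: 10% yearly turnover, Poisson or gamma-Poisson visits, and screening only when there was no AUDIT-C in the prior 365 days. Visits per year are not given. A rough floor is 1,205 × 19 × 13 / 381,550 = 0.78, because that denominator is all patients of the health system. I used 1 to 4.

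Sustainment/active ratio of monthly BI rates, with BI only at screening visits:

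| Visits per year | All due visits screened | Half screened |
|---|---|---|
| 1 | 0.59–0.72 | 0.79–0.87 |
| 2 | 0.50–0.53 | 0.67–0.70 |
| 3 | 0.42–0.43 | 0.56–0.63 |
| 4 | 0.38–0.40 | 0.50–0.55 |

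At 20% uptake the ratio is roughly 0.75 to 1.

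Now let BI also occur at later visits of patients with a past-year positive screen, r times as often as at the screening visit (80% of due visits screened, 2 visits a year):

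| r | 0 | 0.25 | 0.5 | 0.75 | 1 |
|---|---|---|---|---|---|
| Ratio | 0.52 | 0.74 | 0.89 | 0.98 | 1.05 |

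A separately coded run agrees to within 0.08 on the settings in these two tables that it repeated.

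**5. Screening over the same months.** At 80% uptake and 2 visits a year, the share of patients seen with a documented past-year screen goes from 0.89 in month 4 to 0.94 in month 12.

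**6. Calendar adjustment.** At 2 visits a year, full screening and r = 0, a logistic model with site and 4-month calendar terms gives an odds ratio of 0.48–0.54. The calendar terms do not remove the fall. This fit used fixed site effects and no person effect, so it approximates the planned model.

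**7. Where r might lie.** The SAP assumes 5% of screen-positive patients receive BI before implementation and regards this as an upper bound. If unprompted BI stayed at 5%, prompted BI of 20% would mean r = 0.25 (ratio 0.74). For r = 0.75, prompted BI could be only 5/0.75 = 6.7%. Training or a persisting alert could raise r; the documents do not say.

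**The case against.** The strongest reply is that the outcome credits later care. A positive screen keeps a patient eligible for 365 days, so the eligible pool grows after launch. Providers are trained to offer BI to everyone above the drinking threshold, not only on the screening day (Protocol, Addressing stigma). Templated text is captured, and BI at other visit types counts. Whether the alert repeats at later visits is not stated; EHR details and further sensitivity analyses are in an additional file that is not available here. This stands. A reader might infer that the contrast is bound to show a large fall, and the documents do not support that: at r = 0.75 the fall nearly vanishes, and low uptake or infrequent visits shrink it.

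The Protocol also chose the population denominator as least biased, because implementation changes who is screened. That stands too: patients still due in sustainment are disproportionately infrequent attenders, so a due-only analysis cannot replace the main outcome.

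The contrast is secondary and deferred, sustainment versus the pre period also bears on sustained care, and monthly site plots and descriptions of screening by phase are planned. These give context, but none reports who was due.

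**Conclusion.** The concern holds as an interpretive one. The mechanism and its likely direction follow from the documents: annual screening, an alert driven by the screen, few patients screened at launch, and a denominator of all patients seen. The size does not follow. Under the assumed ranges the ratio with unchanged delivery runs from about 0.4 to about 1.05, depending on visit frequency, uptake and BI at later visits. Sustainment versus active implementation therefore cannot by itself be read as evidence of lost delivery.

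Three stronger readings should be resisted:
- The 14-day window is not the main cause, and a 60-day window would not cure the problem.
- The primary before/after contrast averages over the same decline, but its direction is not threatened.
- A reader might extend the point to the treatment outcome, given its one-year look-back for a new diagnosis. That has not been quantified, and no claim is made here.

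**What to change.** Keep the population-based BI outcome as the main measure for this contrast. In the SAP's secondary comparisons, and for Protocol Table 4 item c, add:

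- (a) By phase, the share of patients seen who had no AUDIT-C in the prior 365 days.
- (b) A supportive analysis with the same model, restricted to visits with no AUDIT-C in the 365 days before the visit. The numerator is a positive AUDIT-C that day plus a BI that day or within 14 days.
- (c) A statement that a fall in the all-patients BI rate will be read alongside (a) and (b), and is not by itself evidence of lost delivery.

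The cost is some SAP wording, one descriptive table and one more model on EHR data the trial already collects. The due-only subset over-represents infrequent attenders and omits BI at later visits that the trial outcome counts, so it should be labelled supportive only.
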